Project: TOGETHER – A Couple's Model to Enhance Relationships and Economic Stability

NCT: 04227405

Initial Plan: 3/29/2018

Revised Plan: 11/18/2021

Data Analysis Plan

As a preliminary analysis, each of the outcome scales was summarized at pre, post, and follow-up assessments, using descriptive statistics (mean, standard deviation, scale reliability) for males and females in the whole sample, the treatment group, and the control group.

The main goal of the present RCT was to examine the effectiveness of the intervention. Intervention couples were expected to report significantly better outcomes than the control group upon completion of the workshop and further improvement or maintenance of such changes at the six-month follow-up. Multilevel models were used to test mean differences across time points within the treatment group and across spouses (a dyadic approach). Data were nested longitudinally within individuals, and then individuals were nested within couples. The non-independence of data longitudinally and within couples is accounted for in the multilevel models (Kenny, Kashy, & Cook, 2006).

All analyses were conducted in R (version 3.4.1; R Core Team, 2018). Between-group differences in change were estimated with a piecewise multilevel growth model using all three-time points. The piecewise growth model was specified where the first piece corresponded to the intervention period (pre-test to post-test) and the second piece corresponded to the post-intervention period (post-test to follow-up). We also tested between-group differences in change from baseline to follow-up (pre-test to follow-up). Because participants did not complete the post-intervention and follow-up surveys at the same time (i.e., participants completed the surveys within specific time windows), time was specified as the number of months between assessments and allowed to vary across participants.

The multilevel approach utilizes all data from each time point, retaining as much data as possible when attrition occurs. Analyses controlled for demographic variables that have been associated with relationships (for a review, see Karney & Bradbury, 2020) and financial outcomes (Xiao et al., 2015): Race (White = 1 vs. not), marital status (married = 1 vs. not), gender, age, highest level of education, income, length of relationship in years, number of children, and baseline measurement of the outcome variables. We controlled for baseline differences in the outcome measures in the piecewise multilevel growth model by constraining baseline treatment and group to equality (i.e., constrained longitudinal data analysis; Liang & Sieger, 2000). To facilitate the interpretation of results, we computed Cohen's d effect sizes (group mean difference divided by the pooled within-group standard error) and confidence intervals (CI) for all effects. The Benjamini-Hochberg method (1995) was used for adjusting p values for multiple comparisons as recommended by What Works Clearinghouse for controlling the false discovery rate for studies that have multiple outcome variables.

We used multilevel generalized mixed models for attrition analyses where the outcome variable was a binary indicator of missing. Covariates were demographic variables and baseline measures of outcome measures. As in the main analyses, random effects were included to account for the nesting of individuals within couples. Attrition analyses examined if there were significant differences in demographic and outcome variables between all participants that stayed in the study in comparison with those that dropped out. Differential attrition analysis examined if there were significant differences in demographic and outcome variables between the control group's attrition and the intervention group's. Nonetheless, we accounted by any attrition differences by

including demographic variables as covariates and controlling for baseline measures of the outcomes in all of the analyses.

Relatedly, we assessed baseline equivalence across groups for demographics and outcome variables not only in the entire sample (at initial randomization) but also in the analytic sample (retained at follow-up) to evaluate attrition effects. We controlled for baseline differences in demographic and outcome variables in all analyses.

References

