##### **Control Couples: Follow-Up Survey/Financial Literacy Workshop**

Six months after control couples will be invited to come 90 minutes before the Financial Literacy Workshop that will be offered for them. Trained program staff will provide tablets for these couples to complete the follow-up survey in Qualtrics before the beginning of the workshop. Completion of follow-up survey will take about 90 minutes. The trained program staff will provide the couple their compensation in gift cards \$80 per couple (\$40/partner) for assessments and will ask partners to sign the Gift Card Receipt Form. After the participants complete the follow-up survey, they will be invited to attend a three-hour Financial Literacy Workshop (FLW), led by

workshop facilitators at VT, UMD, FSI or designated locations. FLW is a three-hour financial management class to improve financial management knowledge and skills based on Money Smart curriculum by the Federal Deposit Insurance Corporation.

For couples that cannot attend the meeting in person, the questionnaires will be mailed to them with instructions on how to complete them and return them to the program in a self-addressed envelope included in the package (see Instructions for Mailed Follow-up Survey in Attachments). Upon receipt of questionnaires by program staff, the gift cards and Gift Card Receipt Form will be mailed to the couple with instructions to complete the form and mail it back to the program staff in the self-addressed envelope provided (see Letter and Instructions for Completion of Gift Card Receipt Form in Attachments). Couples may also choose to complete the follow-up survey online in which case we will be emailing to each partner the link and their individual passcode and we will be mailing the gift cards or provide them electronically, if this option is available and the couple agrees to it, once they complete the questionnaires.

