#### **Intervention Couples: TOGETHER Workshop**

Couples will begin the TOGETHER workshop at UMD, VT, FSI, or designated agencies, schools, or churches. TOGETHER is a 20-hour psychoeducational program for couples that supports the personal wellbeing, couple relationship, parenting, and financial literacy and management.

TOGETHER was developed by [name] (PI) and the late [name] as part of the emerging interdisciplinary field that integrates relationship education with financial education (Falconier, 2015). TOGETHER adapted the Couples' Coping Enhancement Training (CCET) program developed by [name] (Bodenmann, 1997) and whose effectiveness in improving stress management, communication, and relationship satisfaction has been supported in various studies (Bodenmann & Shantinath, 2004; Lederman, Bodenmann, & Cina, 2007; Shaer, Bodenmann, & Klink, 2008) to financially distressed couples by applying CCET content to financial issues and incorporating financial education. The workshop aims at reducing financial stress and improving relationship functioning by providing couples with knowledge and skills on stress management, communication, conflict resolution and management, problem-solving, and financial management.

The TOGETHER workshop has 9 modules and is designed to be delivered in groups of four to eight couples for 20 hours: 8 weekly sessions of 2.5 hours each. Each session is co-led by two facilitators: a financial counselor and a couples therapist. Each session includes a warm-up activity, brief review of past session content and homework, presentation and practice of new content, summary of all contents covered in the session, and assignment of new homework. After each session, couples are assigned homework so that the skills learned in the session can be practiced between sessions. The TOGETHER curriculum has been pilot tested and results have been published in 2015 in the Journal of Marital and Family Therapy. FSI and TWC will hire couple therapists and financial counselors to provide these workshops. Couple therapists and financial counselors will be trained by [name] and [name].

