The TOGETHER workshop will be offered at FSI, UMD, VT, or designated agencies, schools, or churches. There will be eight offerings in each facility per year. The workshop will be offered in eight sessions (2 hours and 30 minutes each) scheduled on the same day of the week and at the same time. Efforts will be made to offer the sessions in the evenings and on weekends to facilitate participation. Participants complete a 2 minute-session evaluation and a 2-minute homework evaluation within the time allotted to the session. In the last session they complete a 5 minute session evaluation+overall workshop evaluation within the session (see Session Evaluation questionnaire, homework evaluation questionnaire, and session evaluation and overall workshop evaluation questionnaire).

At the first TOGETHER session, couples will complete the Pre Program Survey (nFORM) and the Pre-test Assessment (Qualtrics) before the session begins. Completion of the Pre Program Survey and Pre-test Assessment will take about 90 minutes. For participants both surveys will be collectively referred to as "Pre-Test Survey". Partners will be instructed to complete these surveys in tablets provided by the group facilitators. Couples will receive compensations for

completing assessments in gift cards \$40 per couple (\$20/partner) and each partner will be required to sign and date the Gift Card Receipt Form upon receipt of the gift cards. TOGETHER session facilitators will oversee the completion of the Pre-Test Survey. Participants that fail to attend the first session of the TOGETHER workshop will be mailed the Pre-Test Survey for their completion (see in attachments these two documents: Instructions for Completion of Mailed Pre-Test Survey for Intervention Couples and the Pre-Test Survey (that shows the paper and pencil format for these two surveys combined: Pre-test Assessment and Pre-Program Survey). Participants will be instructed to return the completed surveys on the second session to receive their gift cards. Couples that wish to complete the pre-test survey online instead will be instructed on how to do so.

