#### **Program Termination**

Individuals may terminate their participation in the program for several reasons. They may have participated in the exit meeting concluding their participation in the TOGETHER program. In such instances, a termination letter will be mailed (see Termination Letter in Attachments).

Individuals may discontinue participation and failed to respond to case manager's contact attempts. In those situations, participants may be invited to withdraw if they are no longer interested in participating in the TOGETHER program. In that case a letter will be mailed to participants (see the following three documents in Attachments: the Letter for Potential Termination of Program Participation for Mailed Follow-up Surveys Not Returned, the Letter for Potential Termination of Program Participation for Intervention Couples when Missed Appointments, and the Participant's Program Withdrawal Letter in Attachments). The case manager will also complete a Case Management and Employment Services Summary form for every couple. This form does not contain participants' identifying information but only participants' ID. The form will be entered by graduate assistants in VT or UMD into the database to be submitted to AVAR for data analysis.

Individuals may also be requested to discontinue participation in the program if it is no longer safe for one or both partners to continue participating in the TOGETHER program (see Termination Letter due to Safety Issues in Attachments).

We are describing in detail all the data that will be obtained from participants. However, only the non-identifiable data will be used for data analysis of program outcomes by AVAR (the local evaluator) and [name] and [name] (PI and Co-PI). The non-identifiable database will be made up of all surveys completed by the participants (Applicant's Characteristics, Demographic Information, Pre-Test Survey, Post-Test Survey, Follow-up Survey, TOGETHER Homework Evaluation, the Evaluation of the TOGETHER session) and the Case Management and Employment Services Summary data completed by the case manager. The rest of data collected from participants will not be part of the database for analysis or used for data analysis. These data are only collected with the purpose of providing services to participants.

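### The SAP's models stop at the couple and omit the intervention arm's workshop groups, so standard errors are too small if post-baseline change is positively correlated within those groups

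*SAP*

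**What the plan says.** The SAP sets out the hierarchy of its models: "Data were nested longitudinally within individuals, and then individuals were nested within couples". It states that longitudinal and within-couple dependence is accounted for and names no other source. Its paragraph on attrition confirms this: "As in the main analyses, random effects were included to account for the nesting of individuals within couples". There is no workshop-group term, group-clustered variance or sensitivity analysis for grouping. The listed covariates describe persons or couples, apart from the baseline value of the outcome.

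The protocol section Intervention Couples: TOGETHER Workshop says the workshop is "designed to be delivered in groups of four to eight couples for 20 hours", with each session co-led by a financial counselor and a couples therapist. The eight sessions are "scheduled on the same day of the week and at the same time". The pre-test comes first: at session one, "couples will complete the Pre Program Survey (nFORM) and the Pre-test Assessment (Qualtrics) before the session begins".

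Control couples have no shared session before their outcomes are measured. Under Control Couples: Follow-Up Survey/Financial Literacy Workshop, their only group session follows completion of the follow-up survey.

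The Program Termination section lists the surveys and the case management summary that form the analysis database, then adds: "The rest of data collected from participants will not be part of the database for analysis or used for data analysis". The visible text of that list, and of Case Management Data for Analysis, names no workshop-group code.

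**The concern.** Couples are randomised individually, but one arm is then treated in groups and the other is not: a partially nested design. Couples in one workshop share facilitators, fellow participants and discussion for eight weeks, so their changes may resemble each other. A couple random effect does not deal with this. It absorbs the group variance but still treats couples from the same group as independent. Constraining the arms to a common baseline does not help either, because the workshop can act only after the pre-test.

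If the correlation is positive, the treatment arm carries less information than the model credits it with. This affects the pre-to-post and baseline-to-follow-up contrasts between arms, and the tests across time within the treatment group that the SAP also describes. The post-to-follow-up contrast is affected only if group effects change after the workshop ends. Benjamini-Hochberg takes the p values as given and cannot repair standard errors that are too small.

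**Working it through.** **Figures in the plan.** The documents state no power calculation, ICC, design effect or alpha, so there is no such figure to reproduce. Enrolment is internally consistent: 20 + 100 + 100 + 100 + 40 = 360 and 180 + 180 = 360 couples per arm.

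**Inputs from the documents.** 360 couples per arm; m = 4 to 8 couples per workshop group; no grouping of controls before follow-up. This gives 360/8 = 45 to 360/4 = 90 workshop groups. The schedule does not narrow m, because "There will be eight offerings in each facility per year" leaves the number of facilities open.

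**Assumptions.** Couple-level ICC of post-baseline change 0.02 to 0.10; two-sided alpha 0.05; equal variances; full attendance; no attrition.

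**Formulas.** Design effect in the intervention arm: DE = 1 + (m − 1) × ICC. Ratio of true to modelled variance: r = (DE + 1)/2 between arms, because only one arm is inflated, and r = DE within the intervention arm. Standard-error shortfall = 1 − 1/√r. Actual type I error of a single test = 2 × (1 − Φ(1.96/√r)). Interval widening after correction = √r − 1.

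**Between-arm contrasts.**

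| m | ICC | DE | √r | SE too small by | Type I error |
|---|---|---|---|---|---|
| 4 | 0.02 | 1.06 | 1.015 | 1.5% | 5.3% |
| 4 | 0.05 | 1.15 | 1.037 | 3.6% | 5.9% |
| 6 | 0.05 | 1.25 | 1.061 | 5.7% | 6.5% |
| 8 | 0.05 | 1.35 | 1.084 | 7.7% | 7.1% |
| 8 | 0.10 | 1.70 | 1.162 | 13.9% | 9.2% |

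**Within-arm tests at ICC 0.05.** For m = 4, √1.15 = 1.072: shortfall 6.7%, type I error 6.8%. For m = 8, √1.35 = 1.162: shortfall 13.9%, type I error 9.2%.

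**Check by simulation.** With 360 against 360 couples and 20,000 runs per cell, between-arm type I error for m = 4, 6 and 8 was 6.0%, 6.3% and 7.1% at ICC 0.05, and 6.9%, 8.0% and 9.2% at ICC 0.10. At ICC 0 it was 5.0% to 5.2%.

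**Non-attendance.** Suppose a fraction p of assigned couples attends at random and groups are not refilled; the documents do not say what happens. Two assigned couples share a group effect only if both attend, so DE = 1 + p² × (m − 1) × ICC. At ICC 0.05:

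| p | m | DE | √r | Type I error |
|---|---|---|---|---|
| 0.75 | 4 | 1.084 | 1.021 | 5.5% |
| 0.75 | 8 | 1.197 | 1.048 | about 6.2% |
| 0.50 | 4 | 1.038 | 1.009 | 5.2% |
| 0.50 | 8 | 1.088 | 1.022 | 5.5% |

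**The case against.** The strongest reply is that the size of the problem rests on an ICC the documents do not supply. With full attendance and ICC 0.02, type I error is only 5.3% to 5.8%. The 9.2% between-arm figure needs groups of eight, ICC 0.10, full attendance and no attrition together, yet the SAP itself plans for attrition. This stands. It limits the size of the error, not its existence or direction under positive correlation.

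A reader might infer that the reported p values are wrong, or that the treatment effects are biased. The documents support neither. Whether change is correlated within groups is unknown, and ignoring positive correlation alters the precision, not the point estimate. Nor does a single-test error of 5.9% to 7.1% translate into a false discovery rate; that effect has not been computed.

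A reader might also infer that the evaluator cannot identify the groups. The text is only silent. Workshop attendance is entered in nFORM, the facilitators' weekly notes carry a client ID, and the section Independent Evaluator Process Evaluation gives the evaluator downloaded nFORM data. No passage says that any of these identifies the specific group. The protocol also describes separate nFORM systems for service and outcome data, so the download may or may not include attendance. An amendment to the data-use statement may therefore prove unnecessary.

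Two further points stand. Intervention pre-tests are scheduled at the first group session under the facilitators' oversight, so a shared-occasion effect at baseline cannot be wholly excluded. And a workshop-group term leaves out correlation through booster sessions of up to 16 couples, facilitators who may lead several groups, and shared case managers.

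**Conclusion.** The concern holds conditionally. The SAP's hierarchy omits a level of clustering that the protocol builds into one arm, and nothing else in the documents repairs it. If post-baseline change is positively correlated within workshop groups, standard errors and p values are too small. At ICC 0 there is no error.

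Under the assumptions stated in the working, between-arm standard errors are 1.5% to 13.9% too small and single-test type I error is 5.3% to 9.2%. Within-arm tests are affected more at the same ICC. At ICC 0.05, between-arm type I error falls to about 5.5% to 6.2% with 75% random attendance and 5.2% to 5.5% with 50%. The error is modest, but it runs in one direction and is cheap to check, so it should be fixed.

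**What to change.** At minimum, add a stated sensitivity analysis in one of two forms: standard errors clustered by workshop group, or a partially nested model with workshop-group random effects on the post-test and follow-up terms in the intervention arm only. Treat controls and never-attending intervention couples as singletons. Use small-sample degrees of freedom (Satterthwaite or Kenward-Roger) for the linear models. Report the estimated group ICC beside the couple-only results. If group membership is available, making this the main model is preferable. The SAP revision (11/18/2021) postdates planned enrolment (to 9/30/20), so any such change should be labelled as made at that stage.

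First confirm that the nFORM attendance records or the facilitators' notes identify the workshop group, and whether the evaluator's download already holds it. If it does not, or if the Program Termination statement bars its use, amend that statement to allow a non-identifying group code. State residual clustering by booster session, facilitator or case manager as a limitation. If group membership was not recorded, state the whole issue as a limitation.

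The cost is up to two group-level variance terms per outcome, some of which may be estimated at zero, plus a re-run and a linkage step. With 45 to 90 groups, a group variance can be estimated. Between-arm intervals widen by about 4% to 8% at ICC 0.05 with full attendance (√r − 1 = 0.037 to 0.084), and by less with non-attendance.

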**Target population in the proposed project is low-income couples, but any couple that wants to participate in the program will be accepted as long as they meet the eligibility criteria: residing in Northern Virginia and Prince George's County and Montgomery County in Maryland, married or cohabiting for at least a year, 18 years of age or older, and English-speaking. Exclusion criteria includes both partners being retired, physical domestic violence (defined as behaviors that frighten, terrorize, manipulate, hurt, humiliate, blame, often injure, and sometime kill, a current or former intimate partner) or feeling unsafe with partner in the last six months, current diagnosis of a severe psychiatric disorder that required hospitalization in the last 12 months, cognitive impairment, or/and severe untreated substance abuse disorder. Couples can participate as long as both partners consent to be part of the program.**

**To conduct the randomized control trial, 360 couples will be enrolled (180 from Northern Virginia and 180 from Montgomery County, Maryland) for the intervention group and 360 couples (180 from Northern Virginia and 180 from Montgomery County, Maryland) for the control group. Within each group (intervention and control), 20 couples will be enrolled in Year 1 (7/1/16-9/30/16), 100 in Year 2 (10/1/16-9/30/17), and 100 Year 3(10/1/17-9/30/18), 100 in Year 4 (10/1/18-9/30/19), and 40 in Year 5 (10/1/19-9/30/20).**

**Recruitment activities will begin on June 1, 2016. Activities will include producing and distributing flyers, brochures, and posters and/or giving presentation in schools, churches, faith-based community centers, child support agencies, TANF offices, WIC agencies, Head Start programs, Healthy Start program, child welfare agencies, community centers, libraries, stores, barber shops, employment centers, Virginia Tech and University of Maryland clinics and cooperative extension centers, and community events. The Women's Center and Family Services Inc. will concentrate on marketing and recruitment efforts from the network of providers and partner organization they are part of. In addition, graduate students will be responsible for setting up social media outlets that will be used for marketing and recruitment purposes and posting calendars with program activities. The program will also be advertised through its own website ([www.togetherprogram.org](http://www.togetherprogram.org)) and online ads.**

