The target geographic areas in this proposal are Northern Virginia (VA) and Prince George's County Montgomery County, Maryland (MD). Even though these areas have high performing health and socio-economic outcomes for both the capital area and the nation, demographics have changed significantly in the past decade and disparities exist among subpopulations and low-income families who struggle even more than before the last recession which occurred between December 2007 lasting until June 2009 (U.S. National Bureau of Economic Research). Although the median household income is high for Northern VA and Montgomery Co., MD (\$93,100 - \$122,238), the cost of living in these areas was 40% above the national average according to the 2010 U.S. Census and self-sufficiency standard for families has increased significantly in the last decades. For example, in Montgomery Co for a family of three the self-sufficiency standard doubled from \$32,016 in 1994 to \$68,086 in 2010 and contrasted markedly with the federal poverty level of \$17,600 for a family of three and the minimum wage job of \$12,792 for the annual full-time salary. Fairfax Community Action Board recommended using the number of people living in households with incomes below 200% as a better indicator of the level of need in those geographic areas as that indicator more closely approximates the level below which people have difficulty meeting their needs without some kind of assistance. In Fairfax Co 16.8% of residents and 18.3% of residents in Montgomery County live in households with earnings less than 200% of poverty, which indicates clearly the large number of families in this region that cannot meet their financial needs and that are at risk for individual, parenting, and relationship problems.

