#### **Intake and Enrollment Meeting, Part I**

The first part of the Intake and Enrollment meeting will last 60 minutes. During the meeting, the case manager will (a) present a detailed program description and obtain voluntary, informed written consent for program participation from both partners; (b) conduct a formal assessment of domestic violence with each partner individually for 10 minutes (see Domestic Violence Protocol section and Domestic Violence Protocol in the Attachments); (c) enroll participants and collect contact information in nFORM; (d) assign couples to intervention or control group through an automated system of randomization that uses only state of residence (Maryland or Virginia) (PTS); (f) provide orientation about program procedures (one orientation for intervention couples and one orientation for control couples, participants will be given the "Welcome Letter and Instructions for Intervention Couples" or the "Welcome Letter and Instructions for Control Couples" and the "Control Group Flowchart for Participants" or "Intervention Group Flowchart for Participants" - See attachments); (g) describe participants with detailed explanation about payment procedures and VT and MD Tax requirements (providing VT and MD Tax requirements letters in attachmetns; and (h) direct and assist intervention and control couples to complete applicant characteristics survey nFORM and demographic information survey in a tablet (please see grant requirements regarding nFORM collection system)

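### State of residence, the only stated randomization factor, is missing from the SAP's outcome models; adding it is an optional improvement with a small expected gain

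*SAP*

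**What the plan says.** The protocol (Intake and Enrollment Meeting, Part I) has the case manager "assign couples to intervention or control group through an automated system of randomization that uses only state of residence (Maryland or Virginia". Its database paragraphs describe the same step as randomizing by place of residence, using contact data held in the Participant Tracking System (PTS). The enrolment paragraph plans that "360 couples will be enrolled (180 from Northern Virginia and 180 from Montgomery County, Maryland) for the intervention group", and gives the same split for control. The Maryland target names only Montgomery County although Prince George's County is also eligible; I read it as the Maryland share. The documents do not say whether assignment is blocked within state.

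The SAP (Data Analysis Plan) itemises its outcome-model covariates as "Race (White = 1 vs. not), marital status (married = 1 vs. not), gender, age, highest level of education, income", then length of relationship, number of children and the baseline outcome. The only nesting is time within individual within couple. For attrition it says "Covariates were demographic variables and baseline measures of outcome measures", and it accounts for attrition differences by "including demographic variables as covariates and controlling for baseline measures of the outcomes in all of the analyses". For equivalence, "we assessed baseline equivalence across groups for demographics and outcome variables". None of these names state, site or residence, and no other part of the SAP does.

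**The concern.** A factor used to assign couples would normally be carried into the analysis. If allocation is balanced within state and the states differ on the outcome, a model without state counts the between-state difference as residual noise. The treatment contrast is actually more precise than the model reports, so standard errors are a little too large and tests a little conservative. Under simple randomization the test keeps its nominal level, and adding state only improves precision.

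The second strand is attrition. The SAP relies on its demographic covariates to deal with attrition differences, and the only itemised list leaves state out. If dropout changed the state mix differently in the two arms, the model would have no state term to correct for it, and a reader could not see from the plan whether retention was examined by state and arm.

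**Working it through.** **Check of the text.** The enrolment figures agree with each other: 180 + 180 = 360 per arm, and by year 20 + 100 + 100 + 100 + 40 = 360. The plan gives no power calculation, SD, effect size, intraclass correlation, dropout rate or state difference, so there is no stated figure to reproduce and every input below is an assumption.

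**Model.** I used a couple-level comparison of one post-baseline score adjusted for baseline, which is simpler than the SAP's three-time-point dyadic model. Total variance is 1 at each time, baseline-to-post correlation ρ = 0.5, the two states are equal in size, and the state gap is the same at baseline and afterwards. State explains a share R² of variance, so the gap is 2√R² = 0.20, 0.45 or 0.63 SD for R² = 1%, 5% or 10%.

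**Precision.**
- Residual variance without state: 1 − ρ² = 0.75.
- Residual variance with state: (1 − R²) − (ρ − R²)²/(1 − R²). For R² = 10%: 0.90 − 0.40²/0.90 = 0.7222.
- Reduction in reported SE: 1 − √(with/0.75).

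**Type I error without state, if allocation is balanced within state.** The model without state uses the pooled slope 0.5. Its estimate therefore has true variance factor 1.25(1 − R²) − (0.5 − R²) = 0.75 − 0.25R², while the model reports 0.75. Type I error = 2[1 − Φ(1.96/√(true/0.75))].

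| R² | Residual variance with state | SE reduction | True factor without state | Type I without state |
|---|---|---|---|---|
| 1% | 0.7475 | 0.17% | 0.7475 | 4.96% |
| 5% | 0.7368 | 0.88% | 0.7375 | 4.81% |
| 10% | 0.7222 | 1.87% | 0.7250 | 4.62% |

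Under balance the true factor without state is already close to the residual variance with state. Most of the apparent gain is therefore a corrected standard error, not a better estimate.

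**What the documents suggest about the gap.** The one like-for-like comparison is "In Fairfax Co 16.8% of residents and 18.3% of residents in Montgomery County live in households with earnings less than 200% of poverty". On that binary measure the gap is (0.183 − 0.168)/√(0.1755 × 0.8245) = 0.039 SD, and R² = (0.039/2)² ≈ 0.04%. It concerns county residents rather than participants, and income only, which is already a covariate.

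**Dropout.** Bias is roughly (between-arm shift in state mix) × gap × (1 − 0.5). A 10-point shift with a 0.4 SD gap gives 0.10 × 0.4 × 0.5 = 0.02 SD; 5 points with 0.2 SD gives 0.005 SD. At an assumed 20% dropout, 288 of 360 couples remain per arm. Splitting a 10-point shift evenly means one arm is 55% one state: 0.55 × 288 = 158.4 of 180 kept (12% dropout) against 129.6 of 180 (28%), with the states reversed in the other arm. A 5-point shift needs 16% against 24%, also reversed. A state difference in dropout that is the same in both arms produces no shift.

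**The case against.** The strongest case against is that this is a preference with little behind it. Every input is assumed, the only documented gap is about 0.04 SD, and at the low end the standard error moves by 0.2%. Race, education and income may absorb part of any state difference. That stands as a limit on importance. It does not remove the mismatch between the stated randomization factor and the analysis.

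Cost is also a fair objection. PTS holds residence but no outcome data. After listing the surveys and the case-management summary that make up the analysis database, the protocol (Program Termination) says "The rest of data collected from participants will not be part of the database for analysis or used for data analysis". The text that follows on nFORM data bars linking personally identifiable information to surveys for research. A two-level code does not identify anyone, but deriving it from contact data may need that link, so the step cannot be called free.

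The intake description in the protocol also speaks of demographic data being entered for randomization. It names no other factor, and the Part I text says only state is used.

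A reader might infer more than the documents support:
- **That the treatment effect is biased or false positives are inflated.** With complete data neither follows. With dropout, it would take a state pattern that differs between arms, and nothing in the documents points to one. The SAP's use of all time points would also tend to reduce any such bias at follow-up.
- **That state was left out of the attrition and equivalence work.** The SAP says only demographics there, so inclusion cannot be told either way.
- **That the gain could be large.** If the gap arose only after baseline, the SE reduction would be 0.7% to 6.9%, but nothing in the documents supports that pattern.

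**Conclusion.** The concern holds as an optional improvement. State is the only stated randomization factor and is absent from the outcome-model covariates and nesting; for attrition and equivalence it is merely not named. Under a constant gap explaining 1% to 10% of variance, ρ = 0.5 and a simplified model, the consequence is a standard error about 0.2% to 1.9% larger than with state. If allocation is balanced within state, type I error is slightly below 5%. The low end is more plausible. If state does not predict outcome, there is little to gain. The dropout route to bias is possible in principle but not shown.

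**What to change.** Add state (Virginia vs Maryland) and state-by-time fixed effects to the outcome models. The SAP revision is dated 11/18/2021 and written in the past tense, so if results already exist, report this as a sensitivity analysis justified by the randomization design, beside the existing models. Name state explicitly in the attrition models and baseline-equivalence checks, report retention by state and arm, and state whether assignment was blocked within state.

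The statistical cost is a few degrees of freedom among 720 planned couples. The practical cost depends on whether a survey in the analysis database already records state; the attachments are not available to check. If none does, a non-identifying two-level code must be carried into the de-identified file. The protocol's access paragraph names roles that hold both the survey data with client IDs and the linkable identifiers, and they could create it. Given the restrictions on linkage and on what may be analysed, and the protocol's commitment to ask the IRB before PTS serves other purposes, that step should be cleared with the IRB first.
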